#### PrEP adherence

High adherence is important for PrEP effectiveness in preventing HIV acquisition. Study staff also will provide brief adherence counseling at each scheduled visit, to mimic "real world" counseling. Data on adherence to the product use regimen will be collected via standardized interviewer-administered questions to ascertain product use. PrEP use will be measured by dispensing records, and self-report through a validated 3-item questionnaire. Clinic and pharmacy records will be used to document PrEP prescriptions at the ANC clinics and IDI Kasangati, abstracted in real time from pharmacy records and entered into an electronic database. Adherence will also be assessed through urine tenofovir drug levels in male partners 3 and 6 months after PrEP initiation. These point of care kits provide an inexpensive and accurate alternative to plasma or DBS to quantitatively measure adherence.

#### PrEP safety

The Partners PrEP Study demonstrated that PrEP (including FTC/TDF) was safe for use in heterosexual men and women in Uganda. There were no statistically significant differences in the frequency of deaths, serious adverse events, adverse events overall, or key laboratory adverse events for those receiving PrEP compared to those receiving placebo (65).

For the purposes of this study, only serious adverse events (SAEs) and adverse events Grade 3 and above related to PrEP use will be obtained. All AEs that result in a clinical hold or permanent discontinuation of PrEP will be reported on the AE Log CRF regardless of grade.

With appropriate permission of the participant, whenever possible, records from all non-study medical providers related to SAEs will be obtained and required data elements will be recorded on study CRFs. All participants reporting an AE will be followed clinically, until the AE resolves (returns to baseline) or stabilizes.

Reporting on adverse events to relevant IRBs will be according to relevant regulations.

#### Retention

Retention measures for pregnant women and male partners will be those regularly used in previous PrEP studies at the IDI Kasangati— reminder calls, text messages, peer support, and home visits when individuals have several missed visits or an abnormal test result. Couples who break up will remain in

the study but have separate clinic visits. We will continue to collect data about sexual behavior and PrEP and ART use. Research procedures for men will include behavioral questionnaires and blood collection to test for tenofovir drug concentration levels among men using PrEP.

### HIV testing

HIV testing will be performed in accordance with Uganda HIV testing algorithms (66). Men who are tested through HIVST will receive confirmatory testing, either at the ANC where their partner receives care or at IDI Kasangati. All counseling and testing approaches will be in accordance with Uganda HIV counseling and testing guidelines.

### Procedures for HIV-positive men

Men who are HIV-positive will receive ART adherence support, clinical monitoring and quarterly refills. A baseline CD4 count will be used to screen for risk of opportunistic infections. Treatment will be provided by local HIV care providers at a clinic of their convenience or at IDI Kasangati. The recommended first line regimen in Uganda is tenofovir-lamuvudine-dolutegravir. Newly initiated partners shall be seen monthly for the first 3 months and quarterly thereafter according to national guidelines. At these visits, adherence to ART, drug intolerance, side effects/toxicities and response to ART will be assessed. POC VL monitoring will occur at the Kingasa enrollment visit, delivery and at the 6 month postpartum visit. POC VL results will be used to support same day adherence counseling.

**Table 3. Data collection to longitudinally assess behavioral factors related to PrEP and ART use among HIV serodiscordant couples in PMTCT B+**

Behavioral data	Assessment tool
HIV-positive women	
Facilitators and barriers to ART use and adherence in women (Aim 2)	Tool piloted in Partners Demonstration Project and past qualitative and quantitative work (47, 67)
Sexual behavior with study partner and other partners	Tool piloted in multiple couples-based HIV prevention services (47, 68)
Internalized stigma	Internalized AIDS-related stigma scale (69) Tool piloted in multiple couples-based HIV prevention services (47, 68)
Fertility desires	Sexual Relationship Power Scale (70)
Relationship power	Conflict Tactics Scale (71, 72)
Intimate partner violence	Rapid Alcohol Screen (71)
Alcohol use	HIV Medication Self-Efficacy Scale (73)
Self-efficacy of ART use	Social Support Questionnaire- Short Form (74)
Social support	Self Reporting Questionnaire 20-item (75)
Symptoms of common mental disorders	Patient Health Questionnaire 2-item (75)
Depressive symptoms	
HIV-negative men	
HIV prevention preferences among men (Aim 1)	Tool piloted in multiple couples-based HV prevention studies (47, 68) Tool piloted in multiple couples-based HIV prevention services (47, 68)
Self-perceived risk of HIV	
Sexual behavior with study partner and other partners	Tool piloted in multiple couples-based HIV prevention services (47, 68)
HIV-positive men	
Sexual behavior with study partner and other partners	Tool piloted in multiple couples-based HIV prevention services (47, 68)

### Follow up study procedures

All data collection will be conducted in a private room in the participant's preferred language, according to the participant's fluency and preference. Women in the intervention and control groups will be asked about their experience providing the intervention arm letter or control arm letter, as well as their partner's testing and outcome at their PMTCT visits. Women in the intervention and control groups whose partners do not come for testing, will be asked whether they discussed HIV testing with their partner, whether their partner was tested elsewhere, the outcome of his test, and whether any social harms resulted.

At each follow up visit, questionnaires will be administered to assess sexual behavior, self-perceived risk, partner testing status, intimate partner violence, relationship power, future fertility desires, self-efficacy, stigma, facilitators and barriers to ART and PrEP, social support, and symptoms of common mental disorders (Table 3).

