In the Kingasa study, we will use a factorial design in order to evaluate both an intervention to increase male partner HIV testing and an intervention for pregnant and postpartum women living with HIV to provide real-time HIV VL load and ART adherence counseling. Specifically, we will evaluate a) whether invitations to wellness visits increase the proportion of male partners who test for HIV and b) whether POC HIV VL tests increase viral suppression among pregnant and postpartum women living with HIV. We will also assess the impact of providing male counselor phone call follow-up to men in the wellness visit arm to encourage linkage to HIV care and prevention after HIV testing. Women will be randomized 1:1:1:1 to receive a) standard of care interventions with an invitation letter for male partners for fast-track visit for HIV testing and laboratory HIV testing for women at enrollment and every 6 months until 12 months postpartum, b) invitation letter for male partners for fast track visit for HIV testing and POC VL tests for women at enrollment and every 6 months until 12 months postpartum; c) invitation letter to male partners for wellness visits and laboratory-based HIV VL testing for women at enrollment and every 6 months until 12 months postpartum; and d) invitation letter to male partners for wellness visits and POC viral load testing for women at enrollment and every 6 months until 12 months post-partum. Women who are randomized to receive POC VL will receive same day ART adherence counseling and those randomized to receive lab based VL will receive VL results at their next visit with ART adherence counseling based on their VL results.

Women in both arms will receive counseling to minimize social harms associated with status disclosure and HIV testing, and additional counseling and referral to social support services when social harms occur. Based on the current Ugandan MOH guidelines to offer HIVST to both HIV-positive and HIV-negative pregnant women in ANC clinics, women in both arms will be provided an HIVST to give to their partner if they choose. They will be trained in the use and interpretation of the HIVST and be given information about HIV testing and prevention and care services, which she will give to her partner.

This study has been designed to address the gap in male partner engagement by using innovative methods to link men to HIV testing, prevention and care, and thus PMTCT outcomes for women.

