### **Power to detect a difference in HIV testing uptake in male partners with 200 women**

Power is 80% to detect an increase in HIV testing of 20-22% in the male partner testing, as shown in Table 4, assuming:

- the test uptake in the standard of care arm is 20-30% (20% observed in MU-JHU's program and anticipating some increase with new MOH program to offer HIVST in ANC programs)
- test uptake in intervention arm is 42-50% (assuming that the broader services offered in the intervention arm through wellness visits will increase HIV testing by 20-22%)
- Power is based on a log-rank test for time from randomization of a pregnant woman to her male partner receiving HIV test in the clinic

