### *Risks*

*Confidentiality.* Although the study site will make every effort to protect participant privacy and confidentiality, it is possible that participants' involvement in the study could become known to others, and that social harms may result (i.e., because participants could become known as participating in a trial involving HIV-positive persons). For example, participants could be treated unfairly or discriminated against, or could have problems being accepted by their families and/or communities.

*HIV testing.* Participants may become embarrassed, worried, or anxious when completing their HIV risk

assessment and/or receiving HIV counseling. They also may become worried or anxious while waiting for their (or their partner's) HIV test results. Couples-based counseling and discussions of study participation may raise issues between partners, particularly related to blame (from HIV-negative men) and potential termination of the partnership. Participants who learn that they have HIV may experience anxiety or depression related to their test results. Individual and couples-based HIV counseling will be provided by counselors and clinicians who have been trained in specific issues related to HIV serodiscordant couples, including stigma, blame, methods to avoid transmission, and available support services.

*ART adherence counseling.* Participants may become embarrassed, worried, or anxious when talking about their emotions and/or experiences. The counseling staff, including peer mothers, will be highly trained to protect participant's confidentiality and privacy while minimizing uncomfortable feelings. Participants may also experience more intense psychological discomfort during counseling sessions or data collection due to disclosure about common mental disorders or fears of intimate partner violence. Steps will be taken to minimize any psychological discomfort by providing ongoing counseling during study visits and access to staff by WhatsApp and telephone, as needed. Lists of referrals are in place to address recent psychological problems needing intervention. Participants who disclose suicidal ideation, or a history of suicide attempt, either through their questionnaire responses or in conversations with study staff, will be immediately linked to further medical care.

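### The explicit social-harm question goes only to women whose partners do not come for testing, so non-violent harm after clinic testing is not directly asked about

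*Protocol*

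**What the plan says.** The Follow up study procedures section of the protocol sets out three layers of questioning.

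- **All women, about the letter and the test.** "Women in the intervention and control groups will be asked about their experience providing the intervention arm letter or control arm letter", and also about the partner's testing and its outcome, at their PMTCT visits.
- **Only women whose partner has not come.** "Women in the intervention and control groups whose partners do not come for testing, will be asked whether they discussed HIV testing with their partner". The sentence goes on to ask "whether their partner was tested elsewhere, the outcome of his test, and whether any social harms resulted".
- **All women, by questionnaire.** "At each follow up visit, questionnaires will be administered to assess sexual behavior, self-perceived risk, partner testing status, intimate partner violence". The list continues with relationship power, stigma, social support and symptoms of common mental disorders, and Table 3 names instruments for several of these.

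Elsewhere, the Summary promises women in both arms "additional counseling and referral to social support services when social harms occur". Under Risks, the HIV testing paragraph says that couples counseling and discussion of participation may raise issues between partners, "particularly related to blame (from HIV-negative men) and potential termination of the partnership". Overall design lists finding ways to minimize social harms among the study's purposes. It names no social-harm endpoint and no comparison of harms between groups.

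**The concern.** Coming to the clinic for HIV testing is the Aim 1 primary outcome, and it occurs after randomization. A harm question asked only where that outcome has not occurred has two weaknesses.

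First, it omits the couples in whom the protocol itself expects some of the trouble. Blame and the end of a partnership are described under Risks as possible results of testing and couples counseling, yet women in that position are not asked the explicit question.

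Second, if the wellness letter works as planned, fewer women in that group are asked. Any count of the item by randomized group would start from unequal ascertainment that the intervention itself produces.

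At stake are the completeness of harm data on a partner-letter strategy in women living with HIV, and the identification of women for the referral promised in the Summary. An analysis plan cannot repair this, because answers never sought cannot be recovered later.

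**Working it through.** The protocol gives no figure for this point, so there is none to reproduce. The check has two parts.

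**1. What is and is not asked when the partner tests at the clinic**

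- Violence: asked of all women at each follow-up visit. No gap.
- Social support, stigma, relationship power, mental-health symptoms: asked of all women at each follow-up visit. No gap.
- Separation, being sent away, unwanted disclosure: no fixed item. These may come up when a woman describes delivering the letter, but nothing requires the question.
- Whether a harm resulted from the letter or the test: explicitly asked only where he did not come.
- Adverse-event reporting (PrEP safety) covers serious events and PrEP-related events, so it does not fill the gap.

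The protocol treats social harm as wider than violence. Eligibility names the two separately, and the enrollment counseling explores being sent away and the relationship ending alongside violence.

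**2. How many women this could affect**

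Inputs, from the power section for male partner testing and its table: standard-letter uptake of 20%, 25% or 30%, with detectable increases of 22, 21 and 20 points. Wellness uptake is therefore 42%, 46% or 50%, which agrees with the stated assumption that "test uptake in intervention arm is 42-50"%. Each letter group has 100 women (two arms of 50).

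Women asked per 100 = 100 − uptake, if the question is decided by final testing status:

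| Uptake, standard / wellness | Asked, standard | Asked, wellness | Ratio | Not asked, of 200 |
|---|---|---|---|---|
| 20% / 42% | 80 | 58 | 58/80 = 0.725 | 20 + 42 = 62 (31%) |
| 25% / 46% | 75 | 54 | 54/75 = 0.720 | 25 + 46 = 71 (35.5%) |
| 30% / 50% | 70 | 50 | 50/70 = 0.714 | 30 + 50 = 80 (40%) |

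**Illustration of direction.** The harm risks here are assumptions, not protocol figures. Harms recorded per 100 randomized = women asked × risk where he does not test.

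- Risk 5% in every woman: the truth is 5.0 vs 5.0 (standard vs wellness). Recorded: 80 × 0.05 = 4.0 vs 58 × 0.05 = 2.9, then 3.75 vs 2.7, then 3.5 vs 2.5.
- Risk 10% after clinic testing and 5% otherwise: the truth in the first row is 20 × 0.10 + 80 × 0.05 = 6.0 vs 42 × 0.10 + 58 × 0.05 = 7.1. In the last row it is 6.5 vs 7.5. Recorded counts are unchanged, so the direction reverses.
- Risk 2% after clinic testing and 5% otherwise: the truth is 4.4 vs 3.74 in the first row and 4.1 vs 3.5 in the last. Wellness is truly lower, but the recorded gap is too wide.
- With women asked as the denominator, the recorded rate is 5% in both groups in all three cases. The mechanical gap disappears, but harm after clinic testing is still not represented.

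**The case against.** The strongest reply is that the protocol already collects most of what matters from everyone: violence, social support, stigma, relationship power and mental-health symptoms at each follow-up visit. Couples who break up remain in the study with separate visits (Retention), so some separations will become known. HIV status disclosure at 6 months post-partum is named under Aim 2. The question about delivering the letter gives every woman an opening to report trouble, and counseling every three months gives another. This stands, and it is why the gap is narrow. It does not close the gap: knowing that a couple parted or that status is known does not show whether this was an unwanted result of the letter or the test.

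A reader might infer that harms after clinic testing are missed altogether. The documents do not support that, because violence is asked of all women whatever the partner does. Nor is the lack of a social-harm row in Table 5 evidence: that table lists no behavioral questionnaires at all, including those the text requires.

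A reader might also infer that the trial will make the wellness letter look safer by about 28%. That does not follow either. The protocol plans no between-group harm comparison. The 28% merely restates the ratio of women asked; it assumes equal harm risk in all women and a denominator of all women randomized. The Risks section's figure of fewer than 5% separating concerns couples after disclosure of a positive test, so it is not a harm rate for all enrolled women.

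Finally, the counts above use final uptake. Men have up to 6 months to enroll, so a woman whose partner tests late may be asked at earlier visits. This lowers the number never asked. An answer given before he tests, however, cannot record harm that follows the test.

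**Conclusion.** The point holds in limited form. As written, the protocol makes its only explicit social-harm question conditional on the Aim 1 outcome. The resulting gap covers non-violent harms, and the attribution of any harm to the letter or the test, among women whose partners test at the clinic.

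At the planning rates, up to 20-30 per 100 standard-letter women and 42-50 per 100 wellness-letter women might not be asked, a difference of 20-22 per 100. These are upper figures that assume the question follows final testing status; earlier visits would reduce them. A tabulation of this item per woman randomized would favor the wellness letter, but that is a caution about possible use, not a planned analysis. The true size of any distortion in harms cannot be derived from the documents.

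**What to change.** Amend Follow up study procedures so that every woman is asked the same social-harm items at the same follow-up visits, whether or not her partner has tested. The items should name the non-violent harms (for example separation, being sent away, unwanted disclosure) and ask whether the woman links the harm to the letter or the test. The questions on discussing testing and on testing elsewhere can stay restricted to women whose partners have not come.

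If harms are tabulated by randomized group, use all randomized women as the denominator. With the item asked of everyone, the ratio of women asked becomes 100/100 = 1.00 instead of 0.71-0.73.

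The cost is a few added questions in interviews already held at every follow-up visit.

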#### HIV seroconversion

Study staff will counsel male partners who seroconvert and refer them to local HIV care providers for ongoing-care and initiation of antiretroviral therapy according to Uganda treatment guidelines. Seroconverters will be asked to remain in the study until completion of the follow up period in order to implement data collection relevant to secondary outcomes -- antiretroviral resistance, POC plasma VL testing and CD4 after HIV seroconversion.

#### Final study visit

Women will be followed for 6 months post-partum and male partners will be followed for 6 months after enrollment into the study. At this time, or when a participant discontinues study participation, they will have a final study visit. Study procedures at this visit will be similar to other follow up visits. All study participants on ART will continue receiving care at a public health clinic of their choice. Participants on PrEP will be referred for PrEP where available through demonstration projects or the public health system.

#### Quantitative surveys

A structured interview administered to all HIV-positive female partners at enrollment will ask about knowledge of the partner's HIV status, disclosure, fertility desires, relationship power, intimate partner violence, social support, and symptoms of common mental disorders. At the enrollment visit for male partners, a structured questionnaire will be administered addressing HIV testing history and experience with HIV testing through the PMTCT program. At six months following enrollment, a structured questionnaire will be administered to women and men about the acceptability of delivering a letter for a wellness visit to their partners and administered to men about the acceptability of wellness visits that integrate HIV testing and linkage to care.

#### Data quality and management

Health information about the mother and child during pregnancy, delivery and after delivery will be documented. Clinic and pharmacy records will be used to document PrEP prescriptions, abstracted in real time from pharmacy records to tablet-based case report forms and entered into an electronic database. Automated legal range checks will be programmed to reduce data entry errors and internal quality control reports will be run monthly. Our team has experience using this data capture method in other studies of HIV prevention.

#### Qualitative data collection

The goal of the qualitative component is to assess the acceptability of community-based ART refills, POC VL and targeted adherence counseling to pregnant women in PMTCT B+ and the wellness visits for male partners. The construct of acceptability is broadly defined to target not only participants' feelings and attitudes toward the intervention, but also their broader experiences with intervention components. This broader scope allows for addressing "how" and "why" questions about intervention dynamics to inform future dissemination and implementation.

Qualitative data collection will consist of 1) in-depth interviews (IDIs) with men and women in the qualitative sample, and 2) field observations of intervention activities.

#### Individual In-depth Interviews

A purposeful sample of 15 women participants receiving POC viral load testing and 15 male partner

participants receiving invitation letters for wellness visits will be identified for the qualitative IDIs (Total: 30 interviews with participants). Variation in age and socioeconomic characteristics will be represented as part of purposeful sampling

IDIs will explore experiences of intervention components from the perspective of individual participants. Examples of questions for women participants receiving intervention components might be what kinds of difficulties they encountered with transport, unintended disclosure or stigma? Examples of questions to be addressed with male partner participants are: 1) How did the wellness visit compare with experiences in clinic? 2) How did the receipt of preventive services during wellness visits impact the decision to test for HIV, if at all? IDIs will be carried out by trained Ugandan research assistants and will be conducted in private locations at clinics or in the community. They will take place in the interviewee's language of choice (Luganda, English) and will be audio-recorded, with permission, and transcribed.

